7.3 Exploratory Endpoints

Exploratory Immunogenicity Endpoints:

- Peripheral antibody responses to epitopes within the influenza virus surface proteins HA or neuraminidase at all collected time points
- Cell-mediated (eg, B cell, CD4+ T cell, CD8+ T cell) responses in a subset composed of approximately half of enrolled subjects using PBMCs at all collected time points

7.4 Sample Size Calculations

Approximately 720 subjects with 60 subjects per study group will be enrolled in the study. Approximately half of enrolled subjects will be selected to provide a blood sample for PBMC collection.

The number of subjects proposed to be enrolled in this protocol is based upon previous experience with similar studies such as the Mix and Match Studies (NCT 01317745 and NCT 01217758) performed by Division of Microbiology and Infectious Diseases/National Institute of Allergy and Infectious Diseases. These prior studies had study groups of similar size that proved to be sufficient to allow the collection of meaningful data, especially with respect to acute solicited AEs and antibody results. While the current study is not designed to test specific hypotheses, Table 7–1 and Table 7–2 indicate the power of the proposed sample size to detect a range of common, immediate postvaccination elicited safety events as well as to meet the success criteria for SPR.

26 February 2018

Protocol: BP-I-16-005 Version 2.0

Table 7–1	Safety – Power for Detecting at Least 1 SAE, MAAE, or a Grade 3
	Safety – I ower for Detecting at Least I SAE, MAAE, or a Grade 5
	Solicited AE

True Event Rate (%)	Power (%) N = 60	Power (%) N = 120
0.1	5.8	11.3
0.5	26.0	45.2
1	45.3	70.1
2	70.2	91.2
3	83.9	97.4
4	91.4	99.3
5	95.4	99.8

Abbreviations: AE, adverse event; MAAE, medically attended adverse event; SAE, serious adverse event. Note: The exact method was used for the calculations in this table.

Note: Serious adverse events and MAAEs will be collected for approximately 12 months after the last study vaccine dose. Note: Solicited AEs will be collected for 7 days after each of the vaccine doses.

Table 7–2	Immunogenicity – Power for Meeting Success Criteria of SPR
-----------	--

Success Criteria (%)	Proportion of Subjects Achieving a Serum HAI Antibody Titer of at Least 1:40 for the Testing Vaccine (%)	Power (%) N = 60	Power (%) N = 120
	90	98.5	>99.9
70	85	81.9	99.0
	80	44.9	79.0

Abbreviations: HAI, hemagglutination inhibition; SPR, seroprotection rate.

7.5 Analysis Sets

The following analysis sets will be used in the statistical analyses.

Full analysis set (FAS): The FAS will consist of all subjects who are randomly assigned to receive IP. All analyses using the FAS will group subjects according to randomized treatment.

Safety set: The safety set will consist of all subjects who are randomly assigned and receive at least 1 dose of IP. Safety endpoint summaries and listings will be performed on the safety set using study group treatment actually received.

Immunogenicity-full analysis set (IFAS): The IFAS will consist of all subjects who are randomly assigned, receive at least 1 dose of IP, and have at least 1 valid postvaccination and

BARDA CSNH5 Influenza Vaccine With Either AS03 or MF59Protocol: BP-I-16-005 Version 2.026 February 2018determinate assay result. As supportive analysis, all the immunogenicity endpoint summarieswill be performed on the IFAS by actual treatments received.

Immunogenicity per-protocol set (IPPS): The IPPS is a subset of the IFAS, where all subjects meet the IFAS criteria and must meet the following criteria:

- have received all the doses of IP to which they were randomly assigned
- have valid and determinate assay result for HAI at Day 43 for Groups A-D and G-J, and Day 163 for Groups E, F, K, L
- have no significant protocol deviations that are determined to potentially interfere with the immunogenicity assessment of IP.

All the immunogenicity endpoint summaries will be performed primarily on the IPPS using treatment actually received.

7.6 Description of Subgroups to be Analyzed

No subgroup analyses are planned.

7.7 Statistical Analysis Methodology

Study data will be summarized with descriptive statistics (mean, standard deviation, median, minimum, maximum, and number of observations) for quantitative parameters and by incidence rates and the corresponding 95% confidence intervals (CIs) for categorical findings as appropriate.

No formal significance testing will be performed. Details of the statistical analyses, methods, and data conventions are described in the statistical analysis plan.

7.7.1 Subject Disposition

Subject disposition will be summarized by study group and will include subjects who are enrolled, randomly assigned, discontinue, and complete the study. For discontinued subjects, reasons for discontinuation will be summarized.

BARDA CSN Protocol: BP-I-16-005 Version 2.0

7.7.2 Analyses of Demographic and Baseline Characteristics

Demographic and baseline characteristics, such as age, gender, race, body weight, height, and medical history will be summarized by study group using descriptive statistics.

7.7.3 Analysis of Primary Endpoints

7.7.3.1 Analysis of Primary Safety Endpoint

Solicited local and systemic reactions (recorded as AEs, Section 6.2.5.2) during the 8 days after each vaccination, inclusive of the vaccination day, will be summarized as a frequency table that includes 95% exact CIs by study group and by the degree of severity (mild, moderate, or severe).

7.7.3.2 Analysis of Primary Immunogenicity Endpoint

The SPR and corresponding 95% CIs of HAI antibody responses against strains contained in the vaccine at Day 43 for Groups A-D and G-J, and Day 163 for Groups E, F, K, L will be summarized for each study group.

7.7.4 Analysis of Secondary Endpoint

7.7.4.1 Analysis of Secondary Safety Endpoint

Serious adverse events, MAAEs, PIMMCs, and AEs leading to study withdrawal will be summarized by study group and system organ class (SOC)/preferred term (PT).

Unsolicited AEs (including clinically significant laboratory and vital sign abnormalities) for 21 days following each vaccination will be summarized by study group, SOC/PT, and further summarized by severity and relatedness.

Clinical safety laboratory abnormalities will be summarized at prevaccination and 7 days after each vaccination by study group.

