12.1 Appendix 1: Schedule of Events

H5 Influenza Vaccine With Either AS03 or MF59

Protocol: BP-I-16-005 Version 2.0

26 February 2018

Table 12–1Schedule of Events, Groups A to D, G to J

Study visit	Screening	V1	V2 ^a	V3	V4	V5 ^a	V6	V7	V8	V9 ^a (EOS)	ET	Unsch
Study day	-14 to -3	1	4	8	22	25	29	43	142	387	N/A	N/A
Window allowance (days)			V1+3 (±1)	V1+7 (±1)	V1+21 (+3)	V4+3 (±1)	V4+7 (±1)	V4+21 (±3)	V1+141 (±7)	V1+386 (±7)	N/A	N/A
Obtain informed consent	Xb											
Vital sign measurements ^c	Х	Х		Х	Х		Х	Х			Х	X ^d
Height and weight	Х	Xe										
Medical history	Х	Xe										
Perform subject interview ^f			Х	Х	Х	Х	Х	Х	Х	Х	Х	Х
Review diary card ^g			Х	Х	Х	Х	Х	Х			X ^h	X ^h
Distribute diary card ^g and review instructions		X DCI		X DCII	X DCIII		X DCIV					
Distribute measuring tool and thermometer and review instructions		Х			Х							
Collect diary card ^g				X DCI	X DCII		X DCIII	X DCIV				
Concomitant medications	X ⁱ	X ^{e,i}	Х	Xj	Xe	Х	Xj	Х	Х	Х	Х	Х
Concomitant vaccinations	X ⁱ	X ^{e,i}	Х	Xj	Xe	Х	Xj	Х	Х	Х	Х	Х
Complete physical examination ^k	Х											
Targeted physical examination ¹		Xe		Х	Xe		Х				Xď	X ^d
Urine pregnancy test (WOCBP)	Х	X ^{e,m}			X ^{e,m}							X ^d
Review inclusion and exclusion criteria	Х	X ^e			X ^e							

Protocol: BP-I-16-005 Version 2.0

H5 Influenza Vaccine With Either AS03 or MF59

26 February 2018

Study visit	Screening	V1	V2 ^a	V3	V4	V5 ^a	V6	V 7	V8	V9 ^a (EOS)	ЕТ	Unsch
Study day	-14 to -3	1	4	8	22	25	29	43	142	387	N/A	N/A
Window allowance (days)			V1+3 (±1)	V1+7 (±1)	V1+21 (+3)	V4+3 (±1)	V4+7 (±1)	V4+21 (±3)	V1+141 (±7)	V1+386 (±7)	N/A	N/A
Venous blood sample collection for clinical safety laboratory tests ⁿ	Х			X°	X ^{e,o}		Xº					X ^d
Venous blood sample collection for antibody assays		Xe			Xe			Х	Х			
Cellular immunology (subset only)		Xe			Xe			Х	Х			
Randomization		X ^e										
Vaccination		Х			Xp							
Monitor subject for 30 minutes following vaccination ^q		Х			Х							
Examine vaccination site ^r		X ^s		Х	X ^s		Х				Xď	Xt
AE/MAAE/PIMMC/SAE assessment ^u		Х	Х	Х	Х	Х	Х	Х	X	Х	Х	Х

Table 12–1Schedule of Events, Groups A to D, G to J

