Abbreviations: AE, adverse event; ALT, alanine aminotransferase; AST, aspartate aminotransferase; DC, diary card; eCRF, electronic case report form; EOS, end of study; ET, early termination; FDA, Food and Drug Administration; MAAE, medically attended adverse event; N/A, not applicable; PIMMC, potentially immune-mediated medical condition; SAE, serious adverse event; SUSAR, suspected unexpected serious adverse reaction; ULN, upper limit of normal; Unsch, unscheduled; V, visit; WOCBP, women of childbearing potential.

^a Telephone call assessment.

^b Prior to the completion of any study-related procedures.

Protocol: BP-I-16-005 Version 2.0

H5 Influenza Vaccine With Either AS03 or MF59

- 26 February 2018
- ^c Vital sign measurements include oral temperature, pulse rate, and blood pressure. Vital signs will be measured before blood is collected, at both pre-vaccination and 30±5-minute postvaccination time points on a vaccination day. Diastolic and systolic blood pressure will be measured after the subject is seated for at least 5 minutes.
- ^d If clinically indicated.
- e Prior to vaccination.
- ^f Ask subject a standard nonleading question to elicit any medically related changes in their well-being. Ask if they have been hospitalized, had any accidents, used any new medications, received any vaccinations, or changed concomitant medication regimens (both prescription and over-the-counter medications).
- ^g Diary Card I (Days 1-8) and III (Days 22-29) will be used to collect unsolicited and solicited local and systemic reactions. Diary Card II (Days 9-21) and IV (Days 30-43) will be used to collect unsolicited AEs.
- ^h If applicable, according to the protocol period, collect and review DC with subject.
- ⁱ Use of all concomitant medications that the subject is taking at the time of Visit 1, medications taken up to 14 days prior to Visit 1, and vaccines received 12 months prior to Visit 1 will be recorded in the subject's eCRF.
- ^j Obtained by interview and by review of diary card completed by the subject.
- ^k Any physical examination findings will be collected in the eCRF for medical history data presentation.
- ¹ Targeted physical examination will be performed at the discretion of the investigator, if necessary, to evaluate AEs or clinical laboratory abnormalities. Any findings from this examination will be collected in the eCRF for AEs.

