All AEs reported after the first dose of IP will be summarized in tables. AEs within 21 days of each dose of IP, and before the date and time of the next dose of IP (if applicable) will be summarized in tables based on each dose only (Dose 1, 2 for Groups A-D, G-J; Dose 1, 2, 3 for Group E, F, K and L). When the time of an AE is missing and the AE start date is on the date of vaccination, then that AE will be considered as happening after the corresponding dose of IP.

All AEs will be summarized by presenting the number and percentage of subjects having any AEs and having each individual adverse event based on SOC and PT, and PT only. At each level of subject summarization, a subject is counted once if the subject reported one or more events. Percentages will be calculated out of the number of subjects as treated per study group in the Safety Set. For the dose-specific AE summaries, percentages will be calculated out of the number of subjects as treated per study group corresponding to Dose 1, Dose 2 or Dose 3.

Unless otherwise stated, AEs will be sorted in descending order by frequency of SOC and PT.

The following summaries, based on Dose 1 only, Dose 2 only, and both Dose 1 and Dose 2 for Groups A-D, G-J and Dose 1 only, Dose 2 only, Dose 3 only, and all Dose 1, Dose 2 and Dose 3 for Groups E, F, K and L will be provided:

- Overview summary of the number and percentage of subjects with any AE, SAE, AE related to IP, AE leading to study withdrawal, AE leading to death, solicited local AE, severe solicited local AE, solicited systemic AE, severe solicited systemic AE, MAAE, PIMMC, unsolicited AE, severe unsolicited AE, and unsolicited AE related to IP
- All AEs by SOC and PT
- All AEs by AE Type and PT
- All AEs by SOC, PT and Severity

- All AEs by SOC, PT and Relationship
- All unsolicited AEs by SOC, PT and Day of Onset

The following summaries with 95% exact CIs using Clopper Pearson method, based on events recorded during the 8 days post each vaccination will be provided as the analysis of primary safety endpoint:

- Solicited Local AEs by Severity
- Solicited Systemic AEs by Severity

All MAAEs and PIMMCs after the first dose of IP will be summarized in a table by SOC, PT and Severity.

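### SAP 9.1 counts an untimed adverse event dated on a vaccination day as post-dose even when it was found in a pre-dose sample or reading, which inflates the later dose in the by-dose tables

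*Protocol*

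**What the plan says.** Protocol 7.7.4.1 counts as unsolicited AEs, by study group, "Unsolicited AEs (including clinically significant laboratory and vital sign abnormalities) for 21 days following each vaccination". The same section also says: "Clinical safety laboratory abnormalities will be summarized at prevaccination and 7 days after each vaccination by study group".

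The schedules show what is done before the injection on a vaccination day:

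- **Laboratory, Groups A-D and G-J.** In Protocol Table 12-1, the Visit 4 cell of the row "Venous blood sample collection for clinical safety laboratory tests" carries the footnote for procedures done before vaccination. SAP Table 14-1 repeats it.
- **Laboratory, Groups E, F, K, L.** In Protocol Table 12-2, the Visit 4 and Visit 8 laboratory cells carry no such footnote, although the antibody-sample cells at those visits do. For these groups the pre-dose timing of safety laboratory draws rests on 7.7.4.1.
- **Vital signs, all groups.** Footnote c of both tables has them measured "at both pre-vaccination and 30±5-minute postvaccination time points on a vaccination day".

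SAP 9.1 builds the by-dose AE tables from events that start within 21 days of a dose and before the next one. It then sets a default for an event that lacks a clock time and starts on a vaccination day: "that AE will be considered as happening after the corresponding dose of IP". No exception is given. SAP 9.1 also splits unsolicited AEs by day of onset from each dose, at 1-8 days and later than 8 days. Protocol 6.2.5.4 lists time of onset among the items collected for every AE.

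**The concern.** The default suits an event whose order relative to the injection is unknown. It does not suit an abnormality found in blood drawn, or a reading taken, before the injection, because there the order is known. As written, one Visit 4 sample can appear as prevaccination in the laboratory summary and as post-dose 2 in the AE summary.

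Unsolicited AEs after each dose are a secondary safety endpoint. Every arm receives adjuvanted vaccine and there is no placebo arm, so comparing doses within a group is one of the few internal references available. The error has a fixed direction: it can only add events to the later dose. The onset-day split makes it more visible, because a finding about three weeks after dose 1 is shown as an early reaction to dose 2.

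**Working it through.** No figure in the plan depends on this rule, so there is none to reproduce. The check is a day count followed by an illustration of size.

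**Step 1: where a pre-dose Visit 4 finding belongs.** Nominal elapsed time from dose 1 is 22 - 1 = 21 days. The protocol schedule allows V1+21 (+3), that is 21 to 24 days. The SAP schedule shows V1+21 (±3), that is 18 to 24 days.

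| How the dose-1 window is counted | Visit 4 finding belongs to | Effect of the default |
|---|---|---|
| Elapsed days, visit at or before 21 days | dose 1 | moved from dose 1 to dose 2 |
| With the 21 ± 3 day footnote to SAP Table 4-1 | dose 1 | moved from dose 1 to dose 2 |
| Study Days 1-21 (Diary Card II ends on Day 21), nominal visit | neither dose | added to dose 2 only |
| Elapsed days, visit at 22-24 days, footnote not applied | neither dose | added to dose 2 only |

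Dose 2 is inflated in every row; dose 1 is reduced only in the first two. In every row the finding is placed in the 1-8 day onset category after dose 2.

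**Step 2: where a pre-dose Visit 8 finding belongs (Groups E, F, K, L).** Visit 8 is V1+141 (±7), Days 135 to 149.

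- From dose 2: nominal 142 - 22 = 120 days; minimum 135 - 25 = 110; maximum 149 - 22 = 127 under the protocol's Visit 4 window, or 149 - 19 = 130 under the SAP's.
- From dose 1: 141 ± 7 = 134 to 148 days.

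Both intervals lie far outside 21 days. The default adds the finding to dose 3 and leaves doses 1 and 2 unchanged.

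**Step 3: size.** Let q be the share of subjects with an AE first found pre-dose and dated on that vaccination day, and m the share of those AEs with no clock time. Neither is given in the documents; the ranges are assumptions. The misassigned share is s = q × m, or 60 × s subjects in a group of 60 (Protocol 7.4).

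| q | m | s | Subjects per 60 |
|---|---|---|---|
| 1% | 10% | 0.1% | 0.06 |
| 2% | 10% | 0.2% | 0.12 |
| 2% | 50% | 1.0% | 0.60 |
| 2% | 100% | 2.0% | 1.20 |
| 5% | 100% | 5.0% | 3.00 |

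At dose 2 the rate rises by s, so the dose 2 minus dose 1 difference shifts by s if the finding was not in dose 1's window, and by 2s (0.2 to 10 percentage points) if it was. At dose 3 the rate rises by s (0.1 to 5 points). With m = 0 the error is zero.

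**The case against.** The strongest reply is that this is a fallback for data that should rarely be missing. Onset time is a collected item, and nothing in the documents shows that it is often absent. Assigning untimed same-day events to the dose is also a cautious convention, in line with SAP 9.1 imputing missing severity as severe and missing relationship as related. That defence holds for events of unknown order. It does not reach events that the schedule places before the injection.

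Several further limits stand:

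- Protocol 6.2.5.3 asks sites to report a medical condition rather than a test result where possible, so the AE start date need not be the draw date. Apart from Grade 2 or higher ALT/AST elevations and Grade 4 findings, a laboratory abnormality must be judged clinically significant to become an AE.
- Some pre-dose findings prevent same-day dosing under the protocol, such as fever, an unresolved Grade 3 or higher AE, or a known ALT/AST elevation of Grade 2 or higher. If no dose is given that day, the default does not act.
- The laboratory and vital-sign shift tables by visit are not affected, and no formal comparison between doses is planned.

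A reader might infer two stronger claims. The first is that events move from dose 1 to dose 3; Step 2 rules this out. The second is that the ratio of dose-2 to dose-1 rates turns from about 0.5 to about 2.0. That follows if each draw carries a 2% risk, dose 1 owns two draws (Days 8 and 22; 1 - 0.98² = 4.0%) and dose 2 owns one (2.0%), and the default swaps them: about 29 against 14 of 720 subjects. It needs every time to be missing and Day 22 to belong to dose 1, and it concerns laboratory AEs alone. SAP section 4 also restricts overall columns to tables by randomized treatment, so the as-treated safety tables would not show a pooled 720. It is an upper bound, not an expected result.

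**Conclusion.** The point holds in a limited form. SAP 9.1 gives a wrong by-dose and onset-day assignment for any untimed AE first found in a pre-dose procedure on Day 22 or Day 142. The vital-sign route is explicit for all groups. The laboratory route is explicit for Groups A-D and G-J at Day 22, and rests on 7.7.4.1 for Groups E, F, K and L.

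The likely size is small: a fraction of a subject to three subjects per group of 60 under the assumed ranges, and nothing if times are complete. A loss from dose 1 is possible at Day 22 but not established, because the documents do not settle how day 21 is counted. Through this route, the primary solicited-reaction and seroprotection endpoints, the all-dose AE tables and the by-visit shift tables do not change. It is worth correcting because the direction is fixed and the remedy is cheap.

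**What to change.** Amend the missing-time sentence in SAP 9.1 in three respects:

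1. Apply the default only to AEs with no other information on their order relative to the dose.
2. Where an AE was first identified in a laboratory sample or vital-sign reading taken before the injection on a vaccination day, treat it as preceding that dose. A Visit 4 finding then counts under dose 1 if it is within dose 1's 21-day window. A Visit 8 finding appears in the all-dose tables only.
3. State how day 21 is counted, and whether the 21 ± 3 day footnote to SAP Table 4-1 governs the by-dose tables.

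The cost is a short text change and a blinded check that links the few affected AE records to their laboratory or vital-sign time point. The documents do not describe such a link, so it may have to be made by hand. For Groups E, F, K and L the check should confirm that the draw was in fact pre-dose, since Table 12-2 does not mark it.

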7.7.4.2 Analysis of Secondary Immunogenicity Endpoint

Geometric mean titers and the corresponding 95% CIs of serum HAI and MN antibody responses will be summarized at all collected time points.

BARDA CSNH5 Influenza Vaccine With Either AS03 or MF59Protocol: BP-I-16-005 Version 2.026 February 2018The SPR and corresponding 95% CIs for HAI antibodies will be summarized by study group
at all collected time points.

The SCR and the corresponding 95% CIs for both HAI and MN antibodies will be summarized by study group at all collected postvaccination time points.

7.7.5 Analyses of Exploratory Immunogenicity Endpoint

The exploratory analyses will be described in the statistical analysis plan.

7.7.6 Other Analyses

Prior and posttreatment physical examination findings, the number and percentage of subjects who receive 1, 2, and 3 total doses of IP will be summarized by study group.

7.7.7 Interim Analyses

Interim analyses will be performed based on cumulative immunogenicity and safety data at Day 43 and Day 163 for all study groups. At each time point the study database will be monitored, cleaned, and frozen through the data cut time point. The study team, except the unblinded team members, should remain blind until final database lock and unblinding. Interim analysis results will be unblinded at the group level, and each group will be assigned a fake name. Results will be provided to the sponsor with groups identified only by their fake names.

7.8 Data Quality Assurance

The sponsor will perform quality control and assurance checks on all clinical studies that it sponsors. Before enrolling any subjects in this study, sponsor personnel and the investigator will review the protocol, the package inserts, investigator brochures, the eCRFs and instructions for their completion, the procedure for obtaining informed consent, and the procedure for reporting AEs and SAEs. A qualified representative of the sponsor will monitor the conduct of the study by visiting the site and by contacting the site by telephone and e-mail. During these site visits, information recorded in the eCRFs will be verified against source documents.

Protocol: BP-I-16-005 Version 2.0

7.8.1 Data Management

As part of the responsibilities assumed by participating in the study, the investigator agrees to maintain adequate case histories for the subjects treated as part of the research under this protocol. The investigator agrees to maintain accurate eCRFs and source documentation as part of the case histories. These source documents may include laboratory reports.

Study site staff will enter subject data into Medidata RAVE. The analysis data populations will be a combination of these data and data from other sources (eg, laboratory data).

Clinical data management will be performed in accordance with applicable PPD and/or BARDA standards and data cleaning procedures to ensure the integrity of the data, eg, removing errors and inconsistencies in the data. Adverse events (including SAEs, MAAEs, and PIMMCs) and concomitant medication terms will be coded using the MedDRA and WHODrug dictionaries, respectively.

After database lock, each site will receive a Compact Disc Read-Only Memory (CDROM) containing all of their site-specific eCRF data as entered into Medidata RAVE for the study, including full discrepancy and audit history. Additionally, a CDROM copy of all of the site's data from the study will be created and sent to the sponsor for storage. PPD will maintain a duplicate CDROM copy for their records. In all cases, subject names or initials will not be collected by or transmitted to the sponsor.

BARDA CSN Protocol: BP-I-16-005 Version 2.0

8 Ethics

